### 3.1.2 Dose Escalation

The starting dose of BGJ398 for all subjects not previously treated with BGJ398 will be 75 mg. This dose was based on studies investigating this drug's use in subjects with cholangiocarcinoma, as well as our two patients with TIO who have been treated on Novartis' signature trial. Patients previously treated with BGJ398 will be started on the last dose that they were taking prior to enrolling in this study, based on prior tolerability. While the two NIH patients treated on the Novartis Signature trial (6-9) were treated with 3 weeks on BGJ followed by 1 week off BGJ per cycle, our observations that hyperphosphatemia did not develop in these two subjects suggest that continuous BGJ therapy may be more efficacious in this population. Therefore, subjects will be treated with continuous BGJ398 therapy for six 28-day cycles. FGF23 levels will be measured every 2 weeks. If the FGF23 levels are not suppressed to less than 100 RU/ml on the 6-week outpatient labs, the dose of BGJ398 will be increased to 100 mg once daily after the 8-week NIH visit. The increased dose (100 mg) will be maintained for next 8 weeks. If the FGF23 levels continue to be greater than or equal to 100 RU/ml on the 14-week outpatient labs, the dose of BGJ398 will be increased to 125 mg daily after the-16 week NIH visit for the next 8 weeks. If a subject experiences a significant toxicity (DRAE), the medication will be held and restarted at the previous dose as described in section 3.1.1.

Sample dose modification table:

Dose Escalation Schedule	
Dose Level	Dose of BGJ398
Level 1	75 mg
Level 2	100 mg
Level 3	125 mg

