### 3.1.1 Drug-related adverse events (DRAE)

Drug-related adverse events (DRAE) will be defined as an AE or clinically significant abnormal laboratory value suspected to be related to therapy with BGJ398 (i.e., assessed as unrelated to disease progression, intercurrent illness, or concomitant medications), including those AEs and abnormal laboratory values that result in failure to meet the criteria for re-treatment or to begin a new cycle of therapy.

The criteria for defining DRAE are listed in (Table 3-1) using CTCAE v4.0.

Patients who experience a DRAE will have their therapy with BGJ398 interrupted and will be followed until the toxicity has resolved to CTCAE grade  $\leq 1$  or to the patient's baseline value. After recovery from the toxicity in question, if the investigator believes that it is in the patient's best interest to resume therapy with BGJ398, the patient may resume therapy at a lower dose level.

Prior to enrolling patients into a higher dose level, Grade  $\geq 2$  adverse events should be reviewed for all patients at the current dose level.

Table 3-1 Criteria for defining dose-modifications/interruptions for adverse events

TOXICITY	DRAE CRITERIA
Skipped/ delayed dose	The inability to administer BGJ398 on $\geq 75\%$ of scheduled treatment days during cycle 1 (i.e. $\geq 21$ days for a 28-days daily dosing schedule) due to unresolved adverse event of any grade and considered at least possibly, probably or definitely related to the study drug. Delay in 2 nd cycle administration due to failure of recovery from a possibly, probably or definitely related adverse event to grade $\leq 1$ or baseline by Day 43 (D28 of cycle 1 + 15 days), except for alopecia.
Blood/ bone marrow	Febrile neutropenia CTCAE Grade $\geq 3$ . Neutropenia CTCAE Grade $> 3$ for $> 7$ consecutive days. Thrombocytopenia  - CBC abnormalities CTCAE Grade 3 for $> 7$ consecutive days and/or with signs of clinically significant bleeding.  -CBC abnormalities CTCAE Grade 4. Anemia CTCAE Grade 4.
Renal/ genitourinary	Creatinine CTCAE Grade 1 for $> 7$ consecutive days and blood Pi $> 5.5$ mg/dL and/or blood tCa x Pi $> 55$ mg  /dL  and despite phosphorus lowering therapy for at least 14 days. Creatinine CTCAE Grade 2 for $> 7$ consecutive days. Creatinine CTCAE Grade $\geq 3$ .
Hepatic	Bilirubin CTCAE Grade 2 for $> 7$ consecutive days. Bilirubin CTCAE Grade $\geq 3$ . AST or ALT CTCAE Grade $\geq 3$ .

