### **3.3 DOSE MODIFICATIONS**

For patients who do not tolerate the protocol-specified dosing schedule, dose adjustments are permitted to allow the patient to continue the study treatment. The following guidelines need to be applied:

- These changes must be recorded in the patient's medical records and eCRF.
- All dose modifications should be based on the worst preceding toxicity.

*Abbreviated Title: BGJ398 in TIO*

*Version Date: 21MAY2019*

- Following resolution of toxicity to baseline or  $\leq$  grade 1, treatment is resumed at lower dose of study drug as per Table 3.3.1. If treatment is resumed at the lower dose of study drug, and the same toxicity recurs with the same or worse severity, the patient must discontinue study treatment.

Table 3.3.1 Dose reduction table:

BGJ398 dose level	BGJ398 dose
Starting level (0)	75 mg po once daily
Dose level-1	50 mg po once daily
Dose level-2	25 mg po once daily

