# BGJ398 is administered during the first in patient visit. The patient will be supplied with the drug every 4 weeks for total of 6 months. The patient will be started on 75 mg dose and the dosage changes will be made based on the adverse events and response as described in the protocol.

\*Outside labs may be done at NIH or at outside lab based on patient convenience.

§ V12 (24-weeks) may be done as an inpatient or outpatient visit based on patient convenience. Labs are drawn at the NIH daily (±1 day) for total of 7 lab draws for blood FGF23, 1- 25 (OH)2-Vitamin D, Phosphorous, Calcium, Creatinine and iPTH, Urine Calcium, Creatinine, and Phosphorous.

*Abbreviated Title: BGJ398 in TIO*

*Version Date: 21MAY2019*

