### **7.6 NIH OFFICE OF BIOTECHNOLOGY ACTIVITIES (OBA)/INSTITUTIONAL BIOSAFETY COMMITTEE (IBC) REPORTING CRITERIA: NOT APPLICABLE**

### **7.7 DATA AND SAFETY MONITORING PLAN**

#### **7.7.1 Principal Investigator/Research Team**

The clinical research team will meet on a regular basis, generally weekly, when patients are being actively treated on the trial to discuss each patient. Decisions about dose level enrollment and dose escalation if applicable will be made based on the toxicity data from prior patients.

All data will be collected in a timely manner and reviewed by the principal investigator or a lead associate investigator. Adverse events will be reported as required above. Any safety concerns, new information that might affect either the ethical and or scientific conduct of the trial, or protocol deviations will be immediately reported to the IRB using iRIS.

The principal investigator or designee will review adverse event and response data on each patient to ensure safety and data accuracy. The principal investigator will personally conduct or supervise the investigation and provide appropriate delegation of responsibilities to other members of the research staff.

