#### 11.1.2 Toxicity

BGJ398 showed no evidence of in vitro genotoxicity in Ames and chromosome aberration tests and no evidence of phototoxicity in a 3T3 photo-cytotoxicity test. In vitro safety pharmacology assessment of BGJ398 revealed a decrease in human Ether-à-go-go-related gene (hERG) channel activity with an IC50 of 2.0  $\mu$ M (1121ng/ml).

In vivo safety pharmacology studies in rats and dogs did not reveal any effects on central nervous or respiratory systems and on hemodynamic or electrocardiographic parameters, respectively.

In repeated dose (oral gavage; up to 4-weeks) toxicity studies, BGJ398 did lead to increases in blood FGF23 and blood phosphorous associated with partially reversible ectopic mineralization (kidney, lung, vascular and digestive systems) along with largely reversible changes in renal function parameters and bone growth plate thickening / retention of the primary spongiosa in rats ( $\geq 10$  mg/kg/day) and dogs ( $\geq 10$  mg/kg/day). These effects were deemed to be on-target effects mediated by pharmacological inhibition of FGFR.

In rats, corneal changes were found upon 4 weeks of BGJ398 treatment consisting of irreversible, slight corneal opacity in dose-dependent incidence, as assessed by in vivo ophthalmology, associated with reversible, diffuse epithelial keratopathy at the highest dose of 10 mg/kg. In the 4-week GLP oral toxicity study in rats, the severely toxic dose in 10% (STD10) was considered to

*Abbreviated Title: BGJ398 in TIO*

*Version Date: 21MAY2019*

be at 10 mg/kg/day which resulted in premature death in one (1/30) animal. Doses of 20 mg/kg/day in rats did lead to vasculopathy associated with moribundity after 6 administrations.

In dogs, the highest non-severely toxic dose (HNSTD) was considered to be at 10 mg/kg/day leading to minimal, fully reversible retention of the primary spongiosa and minimal increase in mineralization in lung and kidney without observed functional impairment were observed.

As of data cut-off date September 6, 2016 207 patients have received at least one dose of BGJ398. Forty-three patients were enrolled to dose escalation cohorts and 164 patients to dose expansion arms.

Enrollment to the dose escalation cohorts was as follows: 5mg [N=3], 10mg [N=3], 20mg [N=4], 40mg [N=6], 60mg [N=3], 100mg [N=6], 50 mg bid [N=4], 125mg [N=8], and 150mg [N=6]. MTD was identified to be 125 mg qd on a continuous dosing schedule.

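### Section 3.1.2 triggers both dose increases on FGF23 alone and does not say how they apply to a patient already reduced for toxicity; other sections point the other way, and none says which prevails

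*Combined protocol and SAP*

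**What the plan says.** **The escalation rule (3.1.2).** If FGF23 is not below 100 RU/ml "on the 6-week outpatient labs, the dose of BGJ398 will be increased to 100 mg once daily after the 8-week NIH visit". The second step has the same form: FGF23 still at or above 100 RU/ml at week 14 leads to 125 mg after the week-16 visit. Both steps are worded as mandatory and name fixed doses. The only toxicity sentence in the section covers what to do once a DRAE occurs: hold the drug, then restart at the prior dose, with a reference to 3.1.1.

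**Text that brings toxicity into dosing.**

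- Section 3.3: after recovery, "treatment is resumed at lower dose of study drug as per Table 3.3.1". The same list says that every dose modification rests on the worst toxicity seen so far.
- Section 3.1.1: after a DRAE the patient may resume at a lower level. Before patients are enrolled into a higher level, Grade 2 or higher "adverse events should be reviewed for all patients at the current dose level".
- Section 7.7.1: "Decisions about dose level enrollment and dose escalation if applicable will be made based on the toxicity data from prior patients".
- Schedule of Events, footnote #: "dosage changes will be made based on the adverse events and response as described in the protocol".

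**The link between them (3.1).** The design section refers to 3.1.2 and 3.3 together for escalation and de-escalation and gives no order of precedence.

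**The concern.** A patient reduced for toxicity in the first weeks can still have FGF23 at or above 100 RU/ml at week 6. Section 3.1.2 then names a dose above the one that caused the reduction. Section 3.3 and footnote # suggest that the earlier toxicity should count. The protocol does not say which text the investigator must follow.

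The first stake is patient safety: the same patient could be kept at 50 mg or moved to 100 mg, and each course has support in the text.

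The second is interpretation. Section 7.1 defines a deviation as any departure from the protocol, and Section 8.1 removes patients with major deviations from the per-protocol set. With conflicting rules, not escalating departs from 3.1.2, and escalating arguably departs from 3.3. Which of the two counts as a deviation, and whether it is a major one, is left open. In a trial of 10, one patient is 10% of the sample (1/10).

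**Working it through.** The plan gives no figure of its own on this point, so the check is a comparison of text plus simple arithmetic on the dose levels.

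**1. Inputs.**

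- Escalation table in 3.1.2: 75, 100, 125 mg (levels 1 to 3).
- Table 3.3.1: 75, 50, 25 mg (start, level -1, level -2).
- Trigger: FGF23 not below 100 RU/ml at week 6 (action after week 8) and at week 14 (action after week 16).

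The two tables share only the 75 mg level, and neither refers to the other.

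**2. The literal result for a patient started at 75 mg.**

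- Reduced to 50 mg, then the first step: 100/50 = 2.0 times the current dose; 100/75 = 1.33 times the dose at which the toxicity occurred (100 − 75 = 25 mg above it).
- Reduced to 25 mg, then the first step: 100/25 = 4.0 times the current dose.
- Moved to 100 mg after week 8, a DRAE there, back to 75 mg, then the second step: 125/75 = 1.67 times the current dose and 125/100 = 1.25 times the dose at the DRAE. This case is less firm, because 3.1.2 presumes that 100 mg is held for the full 8 weeks.

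Patients with earlier BGJ398 treatment start at their last dose, so these ratios do not carry over to them.

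**3. Does another section condition the week-8 or week-16 step?**

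- 3.1.2, DRAE sentence: governs the hold and restart, and is silent on the next FGF23-triggered step.
- 3.3, worst preceding toxicity: the closest candidate. It stands in a list of guidelines for patients who do not tolerate the schedule. If it also governs increases, it conflicts with the fixed doses in 3.1.2. If it does not, 3.1.2 stands unqualified.
- 3.1.1, review of adverse events: concerns all patients at a level before others are enrolled higher. It states no consequence for one patient's own step.
- 7.7.1, toxicity data: concerns prior patients, and only where applicable.
- Footnote #: makes dose changes depend on adverse events as well as response, but refers back to the protocol body for how.

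So either these passages do not reach the two steps, or they contradict them. Both outcomes call for reconciliation.

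**4. The restart wording.** For a DRAE at 100 mg, the prior dose (3.1.2) and a lower level (3.1.1) can both mean 75 mg. For a DRAE at the 75 mg starting dose, the escalation table has no prior level, while 3.1.1 and Table 3.3.1 point to a lower one. The cross-reference from 3.1.2 to 3.1.1 therefore leads to a different instruction.

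**5. How many patients?** The expected number is 10 × P(reduced by week 8) × P(FGF23 at or above 100 RU/ml at week 6, given reduced). The documents give neither probability for this population, so the number cannot be computed.

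**The case against.** The strongest reply is that toxicity is well represented in the dosing text. The sentence in 3.3 covers all dose modifications, and 3.1.2 labels its own 75/100/125 mg table a sample dose modification table, so the sentence can fairly be read to include increases. Section 7.7.1 has the team meet about weekly to discuss each patient and has the investigator review adverse event and response data for each patient. Section 3.10.1 lets the investigator take a patient off drug in the patient's best interest. The ladder in 3.1.2 starts at 75 mg, so its silence on reduced patients need not be an order to move them to 100 mg.

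Much of this stands. A reader might infer that the protocol has no toxicity condition on escalation at all; the passages above show that it does bring toxicity in. A reader might also infer that the review in 3.1.1 can never operate. That goes too far, because previously treated patients start at their last dose and so may enter at a higher level. What the reply does not supply is a sentence that ties any of this to the week-8 and week-16 steps, or that says which rule wins.

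Three further inferences are tempting and not supported:

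- **Re-escalation leads to forced discontinuation and a primary-endpoint failure.** The discontinuation rule in 3.3 covers the same toxicity recurring after treatment resumes at the lower dose. It does not address recurrence after a later increase.
- **FGF23 is an unsound trigger, because Section 11.1.2 reports "BGJ398 did lead to increases in blood FGF23 and blood phosphorous associated with partially reversible ectopic mineralization".** That is animal data. Section 1.2 reports decreases in FGF23 in both treated patients with tumor-induced osteomalacia.
- **The 57.5% with hyperphosphatemia in Section 11.1.2 sizes the problem.** It comes from patients with other tumors and counts events regardless of relationship to the drug.

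**Conclusion.** The point holds as a conflict between stated rules with a patient-safety consequence. Section 3.1.2 ties two mandatory, fixed-dose increases to FGF23 alone. It attaches no toxicity condition to either trigger and says nothing about a patient already reduced. Followed literally, it doubles the dose of a patient on 50 mg and places it one third above the dose that caused the reduction. Sections 3.3, 3.1.1 and 7.7.1 and footnote # point the other way, partly in cohort wording that does not settle an individual's step. The restart instructions also disagree for a DRAE at 75 mg.

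The size rests on two assumptions: a patient who started at 75 mg, and a literal reading of 3.1.2. It is the size of the step for one such patient. The documents support no estimate of how often it would occur and no claim about the direction of any effect on the response rate.

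**What to change.** The sponsor and investigator should reconcile Sections 3.1, 3.1.1, 3.1.2, 3.3 and 7.7.1 and footnote # of the Schedule of Events. The amended text should:

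1. State which section prevails at the week-8 and week-16 steps for a patient with an earlier DRAE or a dose reduction.
2. Align the restart wording of 3.1.2 with that of 3.1.1, including for a DRAE at the starting dose.
3. Replace the cohort-style wording in 3.1.1 and 7.7.1 with text that fits within-patient escalation in a single arm.

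Which doses and clinical limits apply is for the sponsor and investigator to decide; none is proposed here.

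The cost is a written amendment. Section 12 requires approval by the manufacturer and the investigator and, where subject safety is significantly affected, by the IRB. The reconciliation itself requires no new visit, sample or change to the planned analyses.

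### Sections 3.1.1, 3.1.2 and 3.3 do not give one consistent restart dose after a drug-related adverse event, and the reduction table has no row for 100 or 125 mg

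*Combined protocol and SAP*

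**What the plan says.** Three places in the protocol govern restart after a DRAE.

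- **Section 3.1.1 (Drug-related adverse events).** Treatment is interrupted until the toxicity resolves to grade 1 or less, or to baseline. Restart is then conditional: "if the investigator believes that it is in the patient's best interest to resume therapy with BGJ398". Where that condition is met, the section allows that "the patient may resume therapy at a lower dose level". No dose or table is named.
- **Section 3.1.2 (Dose Escalation).** If FGF23 is not suppressed on the 6-week labs, "the dose of BGJ398 will be increased to 100 mg once daily after the 8-week NIH visit". A further step to 125 mg can follow after the 16-week visit. On significant toxicity, "the medication will be held and restarted at the previous dose as described in section 3.1.1". The table here numbers 75, 100 and 125 mg as levels 1 to 3. Patients treated with BGJ398 before the study start on their last earlier dose, which need not be 75 mg.
- **Section 3.3 (Dose Modifications).** After resolution, "treatment is resumed at lower dose of study drug as per Table 3.3.1". The table runs from starting level 0 at "75 mg po once daily" to "50 mg po once daily" and "25 mg po once daily". If the same toxicity then recurs at the same or worse severity, the patient must stop study treatment.

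Section 3.1 (Study Design) points to sections 3.1.2 and 3.3 together for raising and lowering the dose. No text joins the two tables or says which section prevails.

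**The concern.** Section 3.1.2 relies on section 3.1.1 for a restart rule that section 3.1.1 does not contain. The two also differ on whether restart follows automatically or is a matter of judgement. Section 3.3 adds a third instruction, tied to a table that stops at 75 mg, so the two doses reached by escalation fall outside it.

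Two things are at stake. First, the mandatory stop in section 3.3 is triggered by recurrence at the lower dose, so the dose chosen at restart sets the conditions under which a patient is permanently taken off drug. Second, the gap lies at doses where DRAEs are foreseeable. Section 11.1.2 places most eye disorders at 100 mg or more and reports dose-limiting toxicities in the 100, 125 and 150 mg cohorts. Table 3-1 makes clinically evident corneal or retinal disease of any grade a DRAE.

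**Working it through.** The plan states no figure to reproduce on this point. The check sets the texts side by side and reads off the restart dose that each one gives.

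**Inputs.** Escalation levels 75, 100 and 125 mg (section 3.1.2). Reduction levels 75, 50 and 25 mg (Table 3.3.1). The only shared dose is 75 mg, called level 1 in one table and level 0 in the other.

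**Readings.**
- A: the previous dose in section 3.1.2 is the dose at the event.
- B: it is the preceding escalation level, meaning the dose from which the patient was escalated.
- C: the highest row of Table 3.3.1 below the current dose.

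Section 3.1.1 yields no number in any row; it says only that the dose is lower.

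| Dose at the event | A (3.1.2) | B (3.1.2) | C (Table 3.3.1) |
|---|---|---|---|
| 75 mg, never escalated | 75 mg | none | 50 mg |
| 100 mg, after escalation | 100 mg | 75 mg | 75 mg |
| 125 mg, after two escalations | 125 mg | 100 mg | 75 mg |
| Pre-treated, started at 100 or 125 mg, not yet escalated on study | unchanged | none | 75 mg |

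**Result under A.** Section 3.1.2 contradicts sections 3.1.1 and 3.3 in every row, because both require a lower dose.

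**Result under B.** Sections 3.1.2 and 3.3 agree at 100 mg. At 125 mg they give 100 mg against at most 75 mg, a difference of 125 − 25 − 75 = 25 mg, or a ratio of 100/75 = 1.33. Section 3.1.2 gives no dose for the never-escalated patient at 75 mg or for the pre-treated patient who starts above 75 mg.

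**Discretion.** Section 3.1.1 lets the investigator decide whether to resume. Sections 3.1.2 and 3.3 state resumption without that condition.

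**Link to the mandatory stop.** Under A, the patient has not resumed at a lower dose, so it is unclear whether recurrence triggers the stop. Under B at 125 mg, the stop would be tested at 100 mg, a dose that Table 3.3.1 does not contain. Under C it would be tested at 75 mg or below. Two patients with the same toxicity at 125 mg could therefore reach permanent discontinuation after recurrence at different doses.

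**A limit on the eye-disorder evidence.** By the enrolment figures in section 11.1.2, 164 patients were in 125 mg expansion arms, and 6 + 8 + 6 = 20 were in the 100, 125 and 150 mg once-daily escalation cohorts. That is 184 of 207, or 89%, at 100 mg or more. The concentration of eye disorders there shows that such events are foreseeable at the escalated doses. It does not by itself show a higher rate than at lower doses.

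**The case against.** The best defence is that the sections fit together. Section 3.1.2 cites section 3.1.1, which requires a lower level, and its sentence follows directly on the 75, 100 and 125 mg steps. The previous dose would then naturally be the preceding step, and all three sections point downward. The two tables can be seen as complementary: one runs up from 75 mg, the other down from 75 mg, and section 3.1 names both sections together. On that view a never-escalated patient at 75 mg is simply covered by Table 3.3.1. The study is also single-site with 10 patients, and the team generally meets weekly to discuss each one.

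Much of this stands. The wording in section 3.1.2 is better called ambiguous than flatly opposed to section 3.1.1, and at 100 mg the favourable reading removes the disagreement. It does not remove it at 125 mg, because section 3.3 sends the dose to Table 3.3.1, whose top row is 75 mg. The complementary view also needs a rule for moving from one table to the other, and none is written. Close supervision makes inconsistent handling less likely, but the team would still have to choose between texts.

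A reader might infer a 2.5-fold spread in restart doses, from 125 mg down to 50 mg. That joins the two most strained readings: restarting at the same dose despite the reference to section 3.1.1, and treating the 50 mg row as the first reduction from any dose although the table anchors it to a 75 mg start. Nor can 100 mg be attributed to section 3.1.1, which names no dose.

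**Conclusion.** The point holds as an internal contradiction in the restart instructions. On the reading most favourable to the plan, what remains is 100 mg against at most 75 mg for a patient at 125 mg, and no dose from section 3.1.2 for a never-escalated patient at 75 mg or a pre-treated patient starting above 75 mg. On the literal reading, section 3.1.2 contradicts both other sections at every dose. This rests on the current text alone and on the fact that no passage ranks the sections or joins the tables.

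Three wider conclusions are tempting but not supported:

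- That this undermines the trial's safety rules generally. The DRAE triggers in Table 3-1, the permanent withdrawal criteria in section 3.10.1 and the monitoring committee's oversight are unaffected.
- That it distorts the per-protocol population. Section 8.1 requires 65% of study drug per cycle, and nothing shows how the restart dose enters that figure. The primary analysis uses the intent-to-treat population in any case.
- That it determines the maximum tolerated dose used in sections 3.1.3 and 3.10.1. Neither section defines that term through the restart dose.

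**What to change.** Reconcile sections 3.1.1, 3.1.2 and 3.3 so that a single rule gives the restart dose for every dose a patient can be on, including 100 mg, 125 mg and a pre-treated patient's starting dose. Merge the escalation schedule and Table 3.3.1 into one table with one numbering. State whether restart is at the investigator's discretion, and to which restart doses the mandatory stop on recurrence applies. Which dose applies in each case is for the investigators and the sponsor to decide.

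The cost is amendment wording and one combined table. Sample size, visits and the primary analysis do not change.
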